## **3.2. Study Population**

### **3.2.1. Definitions of Analysis Populations (Analysis Sets)**

#### **3.2.1.1. Safety Population**

The safety population will include all subjects who received at least one aripiprazole lauroxil injection. All analyses will be carried out using the safety population.

#### **3.2.2. Disposition**

The number and percentage of subjects enrolled, subjects in the safety population, subjects who completed the study, and subjects who were prematurely terminated from the study will be summarized by treatment group and overall. For subjects who discontinued from the study, the reasons for discontinuation as recorded in the disposition page will also be presented. Percentage will be calculated based on safety population.

#### **3.2.3. Protocol Deviations**

All major protocol deviations will be summarized and listed.

## **3.3. Demographics and Baseline Characteristics**

Demographics and baseline characteristics (age, sex, race, ethnicity, weight, height, body mass index [BMI]), will be summarized by treatment group and overall. Categories for missing data will be provided as necessary. Prior antipsychotic medications (risperidone LAI or paliperidone palmitate) and its associated dose level or frequency count at last dose, primary and secondary transition reasons, aripiprazole lauroxil dose at initial injection and last injection, caregiver paid or non-paid will also be summarized by overall subjects.

Medical and psychiatric history will be summarized and listed by treatment group and overall.

## **3.4. Treatment Adherence Rate and Extent of Exposure**

All dosing and exposure information will be included in supportive listings. Cumulative number of injection by treatment group and overall for the safety population will be summarized. The categories of dose change will be also summarized.

### **3.5. Efficacy Analyses**

#### **3.5.1. Clinical Global Impressions-Severity (CGI-S)**

The Clinical Global Impressions – Severity (CGI-S) and the change from baseline at each visit will be summarized by treatment group and overall using descriptive statistics. A plot of mean (SE) of CGI-S score over time will be displayed for all subjects. The one-sample T test at the end of treatment period will be conducted to see if the change from baseline is different from zero. The T-test will be only applied to all subjects.

#### **3.5.2. Brief Psychiatric Rating Scale (BPRS)**

The Brief Psychiatric Rating Scale (BPRS) total score and the change from baseline at each visit will be summarized by treatment group and overall using descriptive statistics. A plot of mean (SE) of BPRS total score over time will be displayed for all subjects. The one-sample T test at the end of treatment period will be conducted to see if the change from baseline is different from zero. The T-test will be only applied to all subjects. The score of unreported item will be imputed with the average of all other items at the same visit.

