### 6.3. Subject Withdrawal

A subject may be discontinued from the study at any time if the subject, investigator, or sponsor determines that it is not in the best interest of the subject to continue participation. Reasons for discontinuation include:

- AE
- Lost to follow-up
- Lack of Efficacy
- Withdrawal by subject
- Non-compliance with study drug
- Other
- Pregnancy
- Protocol deviation
- Study terminated by sponsor

Subjects completing all visits up to and including Day 169 will be considered completers.

If a subject withdraws from the study for any reason, any ongoing AEs will be followed until resolution, until deemed stable by the investigator, or until the subject is deemed by the investigator to be lost to follow-up. If, in the opinion of the investigator, it is necessary to monitor a subject beyond the final study visit, the study period may be extended as necessary. In such instances, the sponsor and the investigator will agree to an acceptable schedule.

In the event that a subject chooses to withdraw from the study, the investigator should make a reasonable effort to ascertain the reason(s) for withdrawal, while fully respecting the subject's rights. Subjects are to be asked to return to the clinic for an ET visit. If the subject fails or refuses to return to the study center, an attempt must be made to contact the subject by telephone in order to assess as many safety and efficacy parameters as possible. All data collected over the telephone must be documented and kept in the subject's record.

The investigator must maintain a record of all subjects who fail to complete the study. The reason for study discontinuation will be made on the appropriate electronic case report form (eCRF). If a subject is lost to follow-up, a reasonable attempt to contact the subject must be made and documented.

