**Table 1: Schedule of Visits and Assessments (Continued)**

Visit windows (days)	Screening	Treatment Period 						
		Day 1	Month 1	Month 2	Month 3 	Month 4	Month 5	Month 6 EOT/ET
		V1	V2	V3	V4	V5	V6	V7
Visit windows (days)		Day 1	22-36	37-64	65-92	93-120	121-148	149-183
Physical Exam 	X	X						
Adverse Event Monitoring	X	X	X	X	X	X	X	X
Concomitant Medication Review	X	X	X	X	X	X	X	X
Vital Signs, Weight, Waist Circumference 	X	X	X	X	X	X	X	X
ESRS-A		X			X			X
Clinical Lab Tests 	X	X	X 	X 	X 			X
Modified MSQ	X 							X 
Modified UKU	X	X						X
CSFQ-14	X	X						X
Injection Site Evaluation 		X	X	X	X	X	X	X
C-SSRS 	X	X	X	X	X	X	X	X
TSR-6-Modified	X	X	X	X	X	X	X	X
CGI-S	X	X	X	X	X	X	X	X
BPRS	X	X	X	X	X	X	X	X
QLS	X				X			X
NSA-16	X				X			X
NY-AACENT	X							X

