**Table 1: Schedule of Visits and Assessments (Continued)**

Visit windows (days)	Screening	Treatment Period 						
		Day 1	Month 1	Month 2	Month 3 	Month 4	Month 5	Month 6 EOT/ET
		V1	V2	V3	V4	V5	V6	V7
Visit windows (days)		Day 1	22-36	37-64	65-92	93-120	121-148	149-183
PSP	X				X			X
BIS	X							X
Burden Assessment Scale	X							X
CarerQOL-7D+VAS	X							X

EOT= end of treatment; ET= early termination; ECG= electrocardiogram; MINI = Mini International Neuropsychiatric Interview; ESRS-A=Abbreviated Extrapyramidal Symptom Rating Scale; MSQ= Medication Satisfaction Questionnaire; UKU= Udvælg for Kliniske Undersøgelser Side Effect Rating Scale; CSFQ-14=Changes in Sexual Functioning Questionnaire Short Form; C-SSRS= Columbia Suicide Severity Rating Scale; TSR-6= Sixth edition of the Treatment Services Review; CGI-S= Clinical Global Impressions-Severity; BPRS= Brief Psychiatric Rating Scale; QLS = Quality of Life Scale; NSA-16 = Negative Symptom Assessment-16; NY-AACENT= New York Assessment of Adverse Cognitive Effects of Neuropsychiatric Treatment; PSP= Personal and Social Performance scale; BIS= Birchwood Insight Scale; CarerQOL-7D+VAS= Caregiver Quality of Life – burden dimensions and visual analog scale

 For all visits other than Screening and Day 1, the visit will be anchored to the previous visit (based on dosing regimen schedule)

 In the event the Month 3 visit is missed or skipped, the additional assessments required at the Month 3 visit (ESRS-A, prolactin, QLS, NSA-16, PSP) should be conducted (via unscheduled assessment) at the subject's next visit

 Visits may be skipped for subjects on a 6 week dosing regimen

 Eligibility Review Form must be reviewed by **PPD** Clinical Surveillance Team (CST) prior to enrolling a subject on Day 1

 Only for prospective subjects who have never received aripiprazole. The oral aripiprazole test doses will consist of 5 mg/day for 2 consecutive days during the screening period. The first test dose should be administered at the clinic.

 Urine drug screen via dipstick at screening. The urine drug screen includes amphetamines, barbiturates, cocaine, methadone, opiates, and phencyclidine. Rescreening may be performed if positive results cannot be confirmed by a history of presumed active substance use or use of prescribed medications, which may account for the positive urine drug test results.

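### The only efficacy tests leave out subjects with no end-of-treatment score and ignore earlier ratings; if dropout depends on outcome, the result can be biased in either direction

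*SAP*

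**What the plan says.** Efficacy is part of the primary objective (Protocol 5.1, SAP 1.1.1). The SAP tests it once per scale. For the BPRS, SAP 3.5.2 says: "The one-sample T test at the end of treatment period will be conducted to see if the change from baseline is different from zero". SAP 3.5.1 has the same test for CGI-S and adds: "The T-test will be only applied to all subjects". No other efficacy test, model or confidence interval is planned. Beyond that, for the BPRS the "total score and the change from baseline at each visit will be summarized by treatment group and overall using descriptive statistics", with a plot of means. CGI-S is handled in the same way.

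**Ratings available.** The BPRS row of Protocol Table 1 reads "BPRS X X X X X X X X": Screening, Day 1 and V2 to V7. The CGI-S row is identical. A footnote adds "Visits may be skipped for subjects on a 6 week dosing regimen", and the 6-week row marks Months 1 and 4 as the visits concerned.

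**Missing data.** The one rule for these scales is at item level, for the BPRS: "The score of unreported item will be imputed with the average of all other items at the same visit". Nothing covers a missing visit. SAP 6.1 takes the CRF visit as the analysis visit and keeps unscheduled measurements out of the summary tables, apart from the potentially-clinically-significant analysis. SAP 3.2.1.1 states: "All analyses will be carried out using the safety population".

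**Early leavers.** The Protocol synopsis and Protocol 6.3 ask them to attend an early-termination (ET) visit with the Day 169 assessments. Table 1 puts ET in the same column as Month 6. Protocol 6.3 then has a fallback that begins "If the subject fails or refuses to return to the study center": a telephone contact to collect what safety and efficacy data it can. AE, lack of efficacy and loss to follow-up are listed reasons for leaving, and Protocol 6.4 rules out replacement. The SAP does not define the end of the treatment period or say whether an ET or telephone score counts towards it.

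**The concern.** A one-sample t-test on a final-visit change can use only subjects who have that final value. The study has no control arm, so the estimate is the mean change of whoever contributes, compared with zero. If subjects who worsen are more likely to leave and do not come back, their loss looks like improvement and nothing in the design separates it from a drug effect. If they do come back, and an early score taken at a bad moment is analysed as end of treatment, the error runs the other way. Either way, the earlier ratings that could correct for selective loss have been collected but are not used in the test. At stake are the size of the reported change on both efficacy scales and the meaning of its p-value.

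**Working it through.** **1. Who enters the test.** A completer enters with the Month 6 score. A leaver who attends ET enters only if ET scores count, which the SAP leaves open. A leaver with neither score is out. Post-dose ratings before Month 6 are V2 to V6, so five on monthly dosing. A 6-week subject may skip V2 and V5, which leaves three (V3, V4, V6). Someone who leaves early has fewer.

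**2. Inputs.** There is no planned figure to reproduce: SAP 2 has no sample-size calculation, and neither document gives an SD, an effect size, alpha or a dropout rate. From the documents: about 50 subjects and six post-baseline visits. Assumed: SD of BPRS change 8, two-sided 5% test (2.5% in the favourable tail), and 20, 30 or 40% leaving early. Negative change is improvement. Two simulations were run:

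- A: 300 trials per case; correlation falling with lag from 0.6; dropout depending on the last observed change; leavers have no final score.
- B: 2,000 trials per case; correlation 0.75 per visit step; log-odds of leaving rising by 1 per SD of worse observed change, or unrelated to outcome; 0, 50 or 100% of leavers attend ET, with the last rating before leaving counted as end of treatment.

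**3. Results for the planned t-test, true change 0.**

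| Case | 20% | 30% | 40% |
|---|---|---|---|
| B, outcome-related, no ET score: n in test | 40 | 35 | 30 |
| – mean change | -0.7 | -1.1 | -1.5 |
| – significant improvement | 9% | 13% | 16% |
| A, outcome-related, no final score: mean change | -1.0 | -1.3 | -1.9 |
| – significant improvement | 12% | 16% | 28% |
| B, outcome-related, half attend ET: mean change | +0.1 | +0.2 | +0.3 |
| B, outcome-related, all attend ET: mean change | +0.8 | +1.0 | +1.3 |
| – significant improvement | 0.3% | 0.2% | 0.1% |

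With dropout unrelated to outcome, B gives means within about 0.07 of zero and significant improvement in 2.2 to 3.1% of trials at every ET attendance. Only sample size is lost. With a true change of -3 and 30% missing, A gives -4.2 from the planned test.

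**4. Hand check at 30%.** The chance of significant improvement is roughly Φ(|bias|/SE − 1.96).

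- A: bias 1.32, SE 1.35; 1.32/1.35 = 0.98; Φ(−0.98) = 0.16, as simulated.
- B: SE = 8/√35 = 1.35; 1.09/1.35 = 0.81; Φ(−1.15) = 0.13, as simulated.

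At 40% the two simulations differ (28% against 16%). The Monte Carlo SE of A's figure is √(0.28 × 0.72/300) = 0.026, so the gap comes from the assumptions and not from noise. That is why the size is given as a range.

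**5. Using all visits.** A likelihood analysis of all visits gave means within about 0.06 of the true zero in every B case and within about 0.1 in A. With a true change of -3 and 30% missing, A gave -2.9. The SE rose by 1.44/1.35 = 1.07 (true change 0) and 1.30/1.20 = 1.08 (true change -3), that is 7 to 8%. Carrying the last score forward did not help: in B it gave +0.8 to +1.4 when dropout followed worse scores.

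**The case against.** **The ET visit may supply the score.** ET shares the Month 6 column and SAP 6.1 follows the CRF visit, so on a plain reading ET scores enter the test and only subjects who miss both visits are left out. This stands: the affected group may be well below 20 to 40%, and the documents give no rate. But that reading brings in the opposite error, because an early score is then analysed as if it were Month 6.

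**The telephone contact.** It is a relevant safeguard, but it cannot be relied on for a full BPRS. In Protocol Appendix D nine of the 18 items are rated from observation at interview, and five of those (3, 6, 7, 13, 16) name an audio recording as a case where rating is not possible.

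**A promise broken?** A reader might infer that the SAP promises every treated subject in the test and then drops some. The text does not support that. The t-test's restriction to all subjects most plausibly means pooled over the three switch-reason groups of SAP 3.1.

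**The numbers favour the remedy.** Both simulations make dropout depend on observed scores, which is missing at random by construction, so a likelihood analysis was bound to do well. No case violates that assumption, CGI-S was not simulated, and the estimators were not exactly the model proposed below. Bias in points also scales with the assumed SD. All of this stands, so the figures are illustrations and not predictions.

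**Enough for a descriptive Phase 4 study.** Protocol 14.4 promises only summaries, and the by-visit n and disposition tables will show how many scores are missing. That makes the loss visible, but the SAP has chosen to test, and the test remains uncorrected.

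**Conclusion.** The point holds with its direction left open. The two t-tests omit any subject without an EOT/ET score, use none of the earlier ratings, and rest on an end-of-treatment value that is not defined.

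A reader might infer that the plan tilts the result towards those who did well. The documents do not establish that. It needs dropout that depends on outcome together with few or unused ET scores. With half the leavers' ET scores counted, the bias in simulation B was at most +0.3 points. With all counted, it turned towards worsening.

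Size, for an assumed SD of 8: -0.7 to -1.9 BPRS points (0.7/8 = 0.09 to 1.9/8 = 0.24 SD) at 20 to 40% without a final score, or +0.8 to +1.3 if all leavers attend ET and are pooled. It is about zero if dropout is unrelated to outcome. The plan should be changed, because the remedy is cheap and uses data already scheduled. Confidence is medium, because every driver of the size is assumed.

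**What to change.** In SAP 3.5.1 and 3.5.2:

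- Make the Month 6 estimate the least-squares mean change with 95% CI from a repeated-measures model on all scheduled post-baseline scores. Use visit and baseline score as fixed effects and an unstructured covariance, with a named simpler fallback such as AR(1) or compound symmetry. The fallback matters: six visits need 6 × 7/2 = 21 covariance parameters from about 50 subjects. Visits skipped on 6-week dosing are then missing by design.
- Assign each ET score to the Table 1 window for its actual study day, and to Month 6 only if it falls in Days 149 to 183. Without this, SAP 6.1 could carry an early ET score into the model as Month 6. Add a rule for ET before Day 22, which no post-dose window covers, and for two scores in one window. State whether telephone scores count.
- Keep the t-test as observed-case support and report how many subjects lack a Month 6 score.
- Add a simple sensitivity analysis to missing at random, for example shifting the values implied for missing Month 6 scores by a stated range of points.

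Cost: SAP text, one model per scale and a little more programming; no new data. The estimate then relies on missing at random, and its SE is slightly larger (7 to 8% at 30% missing in simulation A).

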### **3.6. Quality of Life Analyses**

#### **3.6.1. Personal and Social Performance Scale (PSP)**

Observed values and changes of PSP total score and subscale from baseline values will be summarized by treatment group and overall at each visit using descriptive statistics.

#### **3.6.2. Negative Symptom Assessment-16 (NSA-16)**

Global rating and total score of Negative Symptom Assessment-16 (NSA-16) and the changes from baseline will be summarized by treatment group and overall using descriptive statistics.

#### **3.6.3. Quality of Life Scale (QLS)**

Each 6 subscale of Quality of Life Scale (QLS), total score of 21-items, and the changes from baseline will be summarized by treatment group and overall using descriptive statistics. The score of unreported item will be imputed with the average of all other items at the same visit.

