#### **7.3.14.4. Heinrichs-Carpenter Quality of Life Scale**

The QLS is a clinician-rated scale that is used to assess health-related quality of life and functioning in patients with schizophrenia during the preceding 4 weeks ([Heinrichs, Hanlon et al. 1984](#)) ([Appendix H](#)). The QLS consists of 21 items in 4 major domains (Intrapsychic Foundations, Interpersonal Relations, Instrumental Role, and Common Objects and Activities). Following a semi-structured interview, each item is rated on a 7-point scale, from 0 (severe impairment) to 6 (normal or unimpaired functioning). The QLS will be completed at the time points specified in [Table 1](#).

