### QUALITY OF LIFE SCALE

This instrument is designed to evaluate the current functioning of nonhospitalized schizophrenic persons apart from the presence or absence of florid psychotic symptomatology or need for hospitalization. It assesses the richness of their personal experience, the quality of their interpersonal relations, and their productivity in occupational roles.

It is intended to be administered as a semi-structured interview. Each item consists of three parts. First, a brief statement is provided to help the interviewer understand and focus on the parameter to be assessed. Second, a number of suggested questions are provided that may help the interviewer begin his exploration with the subject. Finally, a seven-point scale is provided for each item, with a brief description at four points to help the interviewer make his judgment and unlabeled points.

The questions provided are just suggestions. They are to be altered or supplemented as needed. Each item should be explored as much as required to allow the rater to make a good clinical judgment. The intent of the schedule is to assess limitations due to psychopathology or personality deficits. Adjustments should be made by the rater when extraneous factors are clearly and unambiguously involved (e.g., decreased social contact due to serious physical illness).

All items should be rated. Circle the appropriate number on each item scale.

---

SCORING: Mean scores of the following subscales and total (prorate items 1 and 12 for missing data as indicated in the manual).

Subscale Scores:

I. Interpersonal Relations (1-8): \_\_\_\_\_

II. Instrumental Role (9-12): \_\_\_\_\_

III. Intrapyschic Foundations (13-17,20,21): \_\_\_\_\_

IV. Common Objects and Activities (18,19): \_\_\_\_\_

III plus IV (13 thru 20): \_\_\_\_\_

Total Score (Items 1-21): \_\_\_\_\_

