### Suggested questions:

Are you especially close with any of the people you currently live with or your immediate family?

0 - Virtually no intimacy

Can you discuss personal matters with them?

1 -

How much have you talked with them?

2 - Only sparse and intermittent intimate interactions

What are these relationships like?

3 -

Can they discuss personal matters with you?

4 - Some consistent intimate interactions but reduced in extent or intensity; or intimacy only present erratically

What sorts of things have you done together?

5 -

When at home, have you spent much time around your family or were you generally alone?

6 - Adequate involvement in intimate relations with household members or immediate family

---

9 - Score here if lives alone and no immediate family nearby

Note: (For Factor and Total Scores, prorate this item on the basis of Items 2 through 8.)

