### Suggested questions:

Did you like your work or schooling?

Would you have preferred to be doing something else?

Do you plan a change? Why?

Did you get good feelings from doing your work – pleasure, fulfillment, etc.

Did your work or school make you feel good about yourself?

Are you enthusiastic about your job?

Do you look forward to going to work?

0 - Pervasive unhappiness and dissatisfaction with occupational role

1 -

2 - Little or no definite evidence of unhappiness or dissatisfaction, but role does not provide any positive pleasure or fulfillment. Perhaps boredom is evident.

3 -

4 - Little or no discontent and some limited pleasure in work

5 -

6 - Rather consistent sense of fulfillment and satisfaction, perhaps in spite of some limited complaints

---

9 - Not applicable if patient not involved in any occupational role functioning

Note: (This item should be rated 2 if item #9 is rated less than 3. For Factor and Total scores, prorate this item on the basis of items 9 through 11.)

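### SAP 3.6.3 imputes a missing QLS item from all other items, but the QLS form prorates item 1 from items 2–8 only and item 12 from items 9–11 only

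*SAP*

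**What the plan says.** SAP 3.6.3 plans descriptive summaries, by treatment group and overall, of "Each 6 subscale of Quality of Life Scale (QLS), total score of 21-items", and of the changes from baseline. It has one rule for missing items: "The score of unreported item will be imputed with the average of all other items at the same visit". The same sentence appears for the BPRS in SAP 3.5.2. SAP Section 5 lists no changes from the protocol.

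The QLS form in Protocol Appendix H gives different instructions for two items. Its scoring block reads "Mean scores of the following subscales and total (prorate items 1 and 12 for missing data as indicated in the manual", and the notes under the two items supply the detail:

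- Item 1 (intimate relationships with household members) has a code 9 outside the rating scale: "Score here if lives alone and no immediate family nearby". The note says "For Factor and Total Scores, prorate this item on the basis of Items 2 through 8". The item belongs to "I. Interpersonal Relations (1-8").
- Item 12 (satisfaction with occupational role) also has a code 9: "Not applicable if patient not involved in any occupational role functioning". Its note prorates the item from items 9 to 11 for factor and total scores. The same note sets item 12 to 2 when item 9 is below 3.

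Protocol 7.3.14.4 says "each item is rated on a 7-point scale, from 0 (severe impairment) to 6 (normal or unimpaired functioning"), so 9 is not a valid score.

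**The concern.** The form says all items should be rated, and items 1 and 12 are the only two with a built-in reason for having no score. A missing value is therefore most foreseeable on exactly the items where the SAP and the form disagree.

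The SAP does not mention code 9. If code 9 counts as unreported, the all-items average replaces the form's within-domain proration. If it counts as reported, a 9 enters an item scored 0 to 6.

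QLS is one of the measures serving the secondary objective on quality of life and functioning, and its subscales are reported outputs. Under the SAP rule, Interpersonal Relations for an affected subject takes in values from the other three domains, so change elsewhere appears as change in that subscale. QLS is collected at screening, Month 3 and Month 6 (Protocol Table 1). If code 9 applies at one visit and not another, a subject with no real change shows one.

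**Working it through.** The documents contain no QLS data and no figure to reproduce. The item scores below are assumed profiles, used only to compare the two rules.

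**Item 1 missing.** Let items 2–8 all equal *a* and items 9–21 all equal *b*.

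- SAP: (7a + 13b)/20. Form: 7a/7 = a.
- Difference on the item, and on the total as a sum: 13(b − a)/20 = 0.65(b − a).
- Difference on the Interpersonal Relations mean (8 items): 0.65(b − a)/8 = 0.081(b − a).
- Difference on the total as a 21-item mean: 0.65(b − a)/21 = 0.031(b − a).

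With a = 2 and b = 3, the SAP gives (14 + 39)/20 = 2.65 and the form 2.00. The subscale is (14 + 2.65)/8 = 2.08 against 16/8 = 2.00.

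| Gap b − a | Item and total (sum) | Subscale mean | Total (21-item mean) |
|---|---|---|---|
| 0 | 0 | 0 | 0 |
| 0.5 | 0.325 | 0.04 | 0.015 |
| 1 | 0.65 | 0.08 | 0.03 |
| 2 | 1.30 | 0.16 | 0.06 |
| 6 (limit) | 3.90 | 0.49 | 0.19 |

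**Change from baseline**, starting from a = 2, b = 3:

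- Code 9 at baseline only, item 1 later rated 2, nothing else changed: subscale (2 − 2.65)/8 = −0.08; total −0.65 as a sum, −0.65/21 = −0.03 as a mean. The form gives zero.
- Code 9 at both visits, items 9–21 each up by 1: the imputed value becomes (14 + 52)/20 = 3.30, so the subscale moves by (3.30 − 2.65)/8 = +0.08 although items 2–8 have not moved.
- Code 9 at both visits with a stable profile: the offset cancels.

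**Group mean.** If 5%, 10% or 20% of subjects had code 9 (assumed), the subscale mean at a one-point gap shifts by 0.05, 0.10 or 0.20 × 0.081 = 0.004, 0.008 or 0.016.

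**If a 9 were kept as a score** (a = 2): subscale (14 + 9)/8 = 2.875 against 2.00; total 9 − 2 = +7 as a sum, 7/21 = +0.33 as a mean.

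**Item 12 missing with item 9 at 3 or above.** Let items 9–11 equal *a* and the other 17 items equal *b*. The SAP gives (3a + 17b)/20, the form a. Only 3/20 (15%) of the SAP value comes from items 9–11.

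- a = 5, b = 3: (15 + 51)/20 = 3.30 against 5.00; Instrumental Role (15 + 3.30)/4 = 4.575 against 5.00.
- a = 4, b = 3: (12 + 51)/20 = 3.15 against 4.00; Instrumental Role (12 + 3.15)/4 = 3.79 against 4.00.

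**The case against.** **Item 12 hardly conflicts.** Its code 9 is for a subject with no occupational role. Such a subject would normally score 0 on item 9, and the form then sets item 12 to 2. With item 9 at 3 or above, a missing item 12 is mostly a rater's omission. This stands: the item 12 figures describe an uncommon case, and the point rests mainly on item 1.

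**A third reading exists.** Code 9 is a recorded response with its own scoring note, so the form could govern code 9 and the SAP rule only blanks. The SAP defers its dataset and programming specifications to separate documents, which could say so. This is possible, but the form's scoring block describes these cases as missing data, so the SAP sentence most naturally covers them. Nothing suggests that a 9 would actually be averaged in; that figure is a conditional side case.

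**Eligibility limits the frequency.** Subjects need a reliable informant and a stable living situation, which makes code 9, and a switch in code 9 during the study, less likely. It does not rule them out: SAP 3.3 provides for paid caregivers, and a stable home can be a home alone.

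**No conclusion would change.** QLS is summarized descriptively; the t-tests are for CGI-S and BPRS. The shifts are small, especially on the mean-score metric that the form uses. This stands as a limit on importance.

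**Leakage between domains affects every item under the SAP rule.** True, but the form gives no proration rule for the other 19 items. All-items averaging there is a choice, not a contradiction.

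**Conclusion.** The concern holds. For a missing item 1, SAP 3.6.3 and the QLS form prescribe different values, and the two agree only when the mean of items 2–8 equals the mean of all 20 other items. For item 12 the conflict is mainly confined to a missing score with item 9 at 3 or above.

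For an affected subject, a domain gap of 0.5 to 2 points moves Interpersonal Relations by 0.04 to 0.16 on a 0–6 scale, and the overall group mean by far less. These sizes rest on assumed profiles and assumed shares of code 9. The finding does not bear on the primary objective or on any planned test. It should be corrected because the stated rule produces subscale scores that the instrument does not yield, and because the treatment of code 9 is left open.

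**What to change.** Amend SAP 3.6.3 as follows:

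1. Treat code 9 on items 1 and 12 as missing, never as a score.
2. For subscale and total scores, prorate item 1 from items 2–8 and item 12 from items 9–11, as Appendix H states.
3. State whether the form's rule setting item 12 to 2 when item 9 is below 3 takes precedence over code 9.
4. Limit the general averaging rule to the other 19 items.

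If the all-items average was intended for items 1 and 12, record and justify the departure in SAP Section 5 instead, and still state how code 9 is handled.

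The cost is a few lines of SAP text and the derivation of two items in the QLS dataset. No new data are needed.
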